10.1 Sample Size Considerations

With a sample size of approximately 20 patients in each cohort, a 95% confidence interval for the proportion of patients experiencing grade III-IV GVHD complications or unexplained prolonged myelosuppression complications in each cohort can be constructed to be within \pm 13.1% of the observed complication proportions. This calculation assumes an expected prevalence of each of these complication proportions of $\leq 10\%$.

Addendum November 2017 Extension of the UCB cohort

The preliminary results in the UCB cohort are encouraging (section 2.6). We therefore have increased accrual to this cohort to a total of **35 patients treated**. This will allow a preliminary assessment of efficacy. Patients who are enrolled but do not undergo treatment (defined as infusion of stem cell product) will be replaced.

Addendum May 2020: In order to further solidify outcomes in the CBU cohort and pending completion of next protocols, we will further increase accrual to this cohort to a total of **60 patients treated**. This will allow a definitive assessment of efficacy. Patients who are enrolled but do not undergo treatment (defined as infusion of stem cell product) will be replaced.

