10.2 Stopping Rules

The occurrence of adverse events that are life-threatening, lead to ICU admission or death (as defined in section 8.3) will lead to temporary suspension of enrollment and immediate assessment of events.

The study will also be paused if there is death that is directly attributed to infusion of adoptive cell therapy; for example severe infusion related reaction, infection from contaminated unit, Grade 5 GVHD etc.

Enrollment may resume upon assessment by the investigators that there are no safety issues and upon appropriate revision of the protocol – if required.

After 10 patients are enrolled in each group, the incidence of the above-defined life-threatening complications will be assessed. If more than one patient out of 10 enrolled patients (i.e., $>10\%$) in a cohort experiences either of these complications, the cohort will be stopped for safety. Each cohort will be evaluated separately with respect to these complications. Additionally, if three or more of the first five patients in a particular cohort experiences either of these complications, the cohort will also be stopped. This is illustrated in the Table below.

N treated subjects	5	10	15	20
No with gr III-IV GVHD to trigger stopping rules	2	2	3	4
No with prolonged myelosuppression to trigger stopping rules	2	2	3	4
No with either Gr III-IV GVHD or with prolonged myelosuppression to trigger stopping rules	3			

For assessment of secondary objectives, descriptive statistics will be utilized via the method of binary proportions and 95% confidence intervals will be calculated to assess the precision of the obtained estimates. All analyses will be performed in SAS Version 9.3 (SAS Institute, Inc., Cary, NC) and Stata Version 13.0 (StataCorp, College Station, TX).

Addendum 5/26/2020: To date stopping rules have not been met in the CBU cohort after enrolling more than 30 patients. The Haplo cohort has not accrued.

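### Section 10.2: the stopping-rule text and its table give opposite decisions on the same data, most clearly at five patients, and count different patients

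*Combined protocol and SAP*

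**What the plan says.** Section 10 defines safety by two complications, grade III-IV GVHD and unexplained prolonged myelosuppression, and calls an incidence above 10% of each unacceptable. Section 10.2 turns this into stopping rules, cohort by cohort.

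- **Ten-patient rule (text).** The assessment takes place "After 10 patients are enrolled in each group". If more than one of the 10 "in a cohort experiences either of these complications, the cohort will be stopped for safety".
- **Five-patient rule (text).** In addition, "if three or more of the first five patients in a particular cohort experiences either of these complications, the cohort will also be stopped".
- **Table.** The text closes with "This is illustrated in the Table below". The column header is "N treated subjects":

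| Row | 5 | 10 | 15 | 20 |
|---|---|---|---|---|
| "No with gr III-IV GVHD to trigger stopping rules" | 2 | 2 | 3 | 4 |
| The same for prolonged myelosuppression | 2 | 2 | 3 | 4 |
| "No with either Gr III-IV GVHD or with prolonged myelosuppression to trigger stopping rules" | 3 | blank | blank | blank |

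The addenda in Section 10.1 separate enrolled from treated: "Patients who are enrolled but do not undergo treatment (defined as infusion of stem cell product) will be replaced". Section 13 has adverse events reported to the DSMB after each successive five patients per arm.

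**The concern.** A table offered as an illustration should give the same decision as the text on every possible set of data. Here it does not. The two complications are the primary safety endpoint, and the five-patient conflict falls exactly when a DSMB report is due. Nothing in the plan says whether text or table governs.

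The cohort mainly exposed is the haplo-identical one, which had not accrued at the May 2020 addendum. For the CBU cohort, that addendum states that the stopping rules have not been met but does not say which version was applied. Both may give the same answer.

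**Working it through.** **Step 1. Derive the table from the text.** Let G and M be the numbers of patients with GVHD and with myelosuppression, and E the number with at least one of them. *Either* can mean pooled (count E) or separate (count G and M each on its own).

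| Look | Text, pooled | Text, separate | Table |
|---|---|---|---|
| 5 | E ≥ 3 | G ≥ 3 or M ≥ 3 | G ≥ 2 or M ≥ 2 or E ≥ 3 |
| 10 | E ≥ 2 | G ≥ 2 or M ≥ 2 | G ≥ 2 or M ≥ 2 |
| 15, 20 | no rule | no rule | 3 and 4 of one kind |

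The text does not reproduce the table's boundary of 2 at five patients on either reading.

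**Step 2. Find the conflicting data.**

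- **A, five patients.** With G = 2 and M = 0 (or the reverse), the table stops. The text continues, because 2 < 3 and its more-than-one rule is not assessed until 10. This holds on both readings. The text never stops at five where the table continues.
- **B, ten patients.** One patient has GVHD and a different one has myelosuppression. The pooled text stops (E = 2). The table continues, because each row shows 1 < 2 and the third row is blank. On the separate reading, text and table agree at ten.
- **Redundant cell.** Any three affected patients include two who share a complication. The third-row trigger of 3 at five patients, the only cell there that matches the pooled text, therefore never acts on its own.

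**Step 3. Size of the disagreement.** The visible text gives no event counts, so the rates are assumptions. Take 10% for each complication (the plan's ceiling) and independence. A patient has at least one with probability 1 − 0.9² = 0.19.

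At five patients:

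- Table: 1 − P(Bin(5, 0.1) ≤ 1)² = 1 − 0.91854² = 0.1563
- Text, pooled: P(Bin(5, 0.19) ≥ 3) = 0.0505. Disagreement: 0.1563 − 0.0505 = 0.1058
- Text, separate: 1 − (1 − 0.00856)² = 0.0170. Disagreement: 0.1392 by exact enumeration

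By ten patients:

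- Table: 1 − P(Bin(10, 0.1) ≤ 1)² = 1 − 0.7361² = 0.4582
- Text, pooled: P(Bin(10, 0.19) ≥ 2) = 0.5932. Disagreement, all of it B: 10 × 9 × 0.09 × 0.09 × 0.81⁸ = 0.1351
- Text, separate: 0.4582. Disagreement: 0

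Sensitivity, as the probability of disagreement:

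| Assumption | At 5, pooled | At 5, separate | By 10, pooled |
|---|---|---|---|
| 5% each, independent | 3.7% | 4.2% | 8.9% |
| 10% each, independent | 10.6% | 13.9% | 13.5% |
| 10% each, complete overlap | 7.3% | 7.3% | 0% |
| 10% each, mutually exclusive | 10.2% | 14.3% | 15.1% |
| 20% each, independent | 20.6% | 34.4% | 6.5% |

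By ten patients the separate reading gives 0% in every row.

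**Step 4. Enrolled or treated (C).** A patient who is never infused cannot have a complication of the infusion. The documents give no ratio of enrolled to infused, so suppose that n of 10 enrolled are infused. At 10% each, independent, the pooled rule fires with probability 1 − 0.81ⁿ − n × 0.19 × 0.81ⁿ⁻¹. This is 59.3% for n = 10, 46.7% for n = 8 and 24.2% for n = 5.

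**The case against.** The strongest defence is a third reading. Rows 1 and 2 would be the more-than-one rule, applied to each complication as Section 10 suggests and acted on as soon as a second case occurs. Row 3 would be the additional pooled rule for the first five, blank afterwards by design. Text and table would then agree through ten patients. The wording does not support this, because the text fixes that assessment at 10 enrolled. The reading also leaves the text's three-of-five rule with nothing to do, although that is already true of row 3 inside the table.

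Other points stand in part.

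- **A is a delay.** Two cases of the same kind in five are still two in ten. In the enumeration the table never stops by patient 10 without the text also stopping. The cost is about five more patients exposed.
- **B is conditional.** It needs the pooled reading, and it may vanish if the blank cell is an artefact of reading the PDF.
- **Rates of 10% or less are not unacceptable under Section 10.** At those rates, part of the gap is the table stopping acceptable cohorts. At 20% each the gap at five patients is wider.
- **Replacement of untreated patients** governs total accrual, as does the treated-patient basis in Section 10.3. Neither changes the count of 10 enrolled in the stopping rule. Only the ten-patient text says enrolled; the five-patient text says patients.
- **Other safeguards exist.** Enrolment is suspended for life-threatening, ICU or fatal events, and Grade IV or fatal acute GVHD is reported immediately (Section 8.3). These do not by themselves cover every grade III GVHD or every prolonged myelosuppression.

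**Conclusion.** The concern holds and must be fixed. Conflict A needs no assumption about rates: two of the first five patients with the same complication stop the cohort under the table and not under the text, on both readings of *either*. Its frequency does rest on assumed rates. With independent complications at 10% each it is 10.6% (pooled) or 13.9% (separate), and the range at 10% each over the dependence patterns examined is 7.3% to 14.3%. Its effect is a delay to the ten-patient look.

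Conflict B, 13.5% by ten patients under independence, depends on the pooled reading and on the blank cell being real. The denominator mismatch is explicit at the ten-patient look, and its effect depends on an infused share that the documents do not give. Where at most one patient is affected, where three or more of five have either complication (pooled), or where two or more of ten share one, text and table agree.

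The practical effect is mainly on the haplo-identical cohort. There is no evidence that a rule was breached in the CBU cohort.

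**What to change.** The sponsor and the DSMB should reconcile text and table into one governing rule.

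1. For each look (5, 10, 15 and 20 treated), state whether each trigger applies to each complication separately or to the two pooled.
2. Fill the blank cells of the third row or mark them not applicable. If two of the same kind already stop the cohort at five, a pooled trigger of three adds nothing.
3. In the ten-patient rule, count treated (infused) patients, as the table does.
4. State which version lay behind the May 2020 statement on the CBU cohort, and check that record against the reconciled rule.

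The documents do not settle which threshold is right, and none is proposed here. The cost is a wording amendment and a short record check, with no extra patients or data. For the haplo-identical cohort this can be done before its first look if it still has not accrued.

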10. STATISTICAL CONSIDERATIONS

The primary objective of this study is to evaluate the safety of adoptive immunotherapy with IPA targeted CBU or with haplo-identical stem cells after conventional induction therapy for very high risk AML or MDS.

The study has 2 cohorts. Patients in cohort 1 will receive CBU cells as adoptive immunotherapy. Patients in cohort 2 will receive haplo identical cells. Both cohorts will be evaluated separately and no formal statistical comparison between cohorts will be performed in this pilot study.

Reinduction therapy in patients with recurrent AML and MDS is extremely toxic with high induction related mortality, which is however justified by the dismal prognosis of patients who don't receive treatment. Safety of the adoptive immunotherapy will be defined as absence of life threatening complications attributable to the adoptive immunotherapy part of the protocol. These are restricted to: 1) grade III-IV GVHD; an incidence of $>10\%$ of this complication in either cohort will be considered unacceptable. 2) Unexplained prolonged myelosuppression, i.e. no count recovery for more than 30 days after completion of chemotherapy, without evidence of residual or recurrent leukemia/MDS. An incidence of $>10\%$ of this complication will also be considered unacceptable.

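### The count-based safety stopping rules end at 20 treated patients, but the CBU cohort now runs to 60

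*Combined protocol and SAP*

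**What the plan says.** Safety is the primary objective. Section 10 names two complications attributable to the cell infusion, grade III-IV GVHD and unexplained prolonged myelosuppression. For GVHD, an incidence above 10% "of this complication in either cohort will be considered unacceptable"; the same limit is set for myelosuppression. Neither limit is confined to the first 20 patients.

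The section 10.2 table makes this operational. The row "No with gr III-IV GVHD to trigger stopping rules" gives 2, 2, 3 and 4 events at 5, 10, 15 and 20 treated, and the myelosuppression row is identical. A combined row has one entry, 3 at 5 treated. There is no later column.

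Section 10.1 was written for about 20 patients per cohort. In November 2017, for the CBU cohort: "We therefore have increased accrual to this cohort to a total of" 35 treated. In May 2020: "we will further increase accrual to this cohort to a total of" 60 treated. The only May 2020 addition to section 10.2 is a status note: "To date stopping rules have not been met in the CBU cohort after enrolling more than 30 patients".

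Two safeguards have no limit on N:
- **Event-driven pause (section 10.2).** Its trigger and effect are given as "adverse events that are life-threatening, lead to ICU admission or death (as defined in section 8.3) will lead to temporary suspension". On restarting, the plan says "Enrollment may resume upon assessment by the investigators that there are no safety issues", with a protocol revision if one is needed.
- **DSMB (section 13).** It receives adverse event reports after every five patients per arm and may recommend termination. No threshold is given.

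**The concern.** Accrual was tripled from about 20 to 60, but the rule that protects those patients was left at its old length. After patient 20, a CBU cohort whose complication rate exceeds the protocol's own limit can run to 60 without meeting any count that stops it.

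The pause does not fill the gap. It is temporary, is lifted on the investigators' assessment, and has no count at which it becomes final. Its scope is also unclear. Section 10.2 refers to the two primary complications with the words "the incidence of the above-defined life-threatening complications will be assessed", which suggests that any one of them could trigger the pause. But the pause points to section 8.3, whose immediate-reporting list is narrower: for acute GVHD, fatal or grade IV; for hematopoietic toxicity, death. Whether grade III GVHD or non-fatal prolonged myelosuppression triggers the pause cannot be settled from the text.

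**Working it through.** **Inputs.** Boundaries 2, 2, 3, 4 at 5, 10, 15, 20 treated (section 10.2); limit 10% (section 10); sample sizes 20, 35 and 60 treated (section 10.1).

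**The plan's own figure.** The 95% half-width at n = 20 and p = 0.10 is 1.96 × √(0.10 × 0.90 / 20) = 0.1315, the stated 13.1 points (truncated). The same formula gives 9.9 points at n = 35 and 7.6 at n = 60; the plan does not restate it.

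**Patients beyond the last boundary.** At full accrual, 60 − 20 = 40. At the May 2020 amendment, at least 60 − 35 = 25 were still to be treated if the cap of 35 had been kept. The number treated is not given in the text reviewed.

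**Recursion, one complication at constant true rate p.** Let f_n(k) be the probability of k events in n treated without having stopped:

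f_n(k) = (1 − p) f_{n−1}(k) + p f_{n−1}(k−1), setting f_n(k) to 0 for k ≥ b_n at each look.

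Check at p = 0.10, n = 5: stop = 1 − 0.9⁵ − 5(0.1)(0.9⁴) = 1 − 0.5905 − 0.3281 = 0.081. Cumulative stopping is then 0.264 at 10, 0.298 at 15 and 0.314 at 20, so the chance of passing 20 is 0.686.

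**Two illustrative extensions**, with looks every five patients from 25 to 60:
- Example 1: 5, 5, 6, 6, 7, 8, 8, 9. Stop when the posterior probability (Jeffreys prior) that the rate exceeds 10% is at least 0.85. This cutoff also reproduces 2, 2, 3, 4 in the current columns.
- Example 2: 5, 6, 7, 8, 9, 10, 11, 12. This continues the table's last ratio, 4/20 = 20%.

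| True rate | Pass 20 | 7 or more of 60, given pass 20 and no other stop | Example 1: later stop given pass 20 (unconditional addition) | Example 2: same |
|---|---|---|---|---|
| 5% | 0.904 | 0.02 | 0.010 (0.009) | 0.001 (0.001) |
| 10% | 0.686 | 0.281 | 0.160 (0.110) | 0.031 (0.021) |
| 15% | 0.449 | 0.685 | 0.500 (0.224) | 0.166 (0.075) |
| 20% | 0.257 | 0.911 | 0.797 (0.204) | 0.431 (0.111) |

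**Other complication present.** If it is independent at 10%, the chance of passing 20 is 0.449 × 0.686 = 0.31 at a 15% rate and 0.257 × 0.686 = 0.18 at 20%. The 3-of-5 combined rule adds nothing once both 2-of-5 rows apply. If the section 10.2 text on more than 1 of 10 is read as a composite of the two complications, the chances are 23% and 13%.

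**Patients still exposed.** Among patients 36 to 60, given passing 20, with the first new look at 40:

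| True rate | No boundary: patients (events) | Example 1 | Example 2 |
|---|---|---|---|
| 15% | 25 (3.75) | 17.3 (2.6) | 23.1 (3.5) |
| 20% | 25 (5.0) | 11.6 (2.3) | 19.1 (3.8) |

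**The case against.** **Oversight does not stop at 20.** This is correct. The pause and the DSMB reports continue, the reports come at the table's own interval, and resumption may require a protocol revision. But neither safeguard has a count, so the outcome rests on judgement alone.

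**The 10% limit may be the continuing rule.** The 2020 note that the rules had not been met after more than 30 enrolled could mean that the limit was still being checked. It could equally mean that the four tabulated looks were passed. The limit cannot simply serve as the missing boundary, because the table lets 2/15 (13%) and 3/20 (15%) continue. A reader cannot tell which standard applies at 25 or 40. Section 2.6 is not in the text reviewed and may hold earlier counts, but sections 10.1 to 10.3 are complete and contain no later boundary.

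**The 45% and 26% chances of passing 20 describe the existing table, not the gap.** This stands. Later columns would not change them. The relevant figures are those conditional on having passed 20.

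**The gain depends on strictness.** This also stands. At a true 15%, Example 2 stops only 17% of cohorts that passed 20, against 50% for Example 1.

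**The rate may not be constant.** The May 2020 amendment added GVHD prophylaxis when donor chimerism exceeds 50% (section 5.5), so cumulative counts would mix patients before and after the change. That qualifies the illustration but does not supply a boundary. The same section reports a high incidence of grade 3 and 4 acute GVHD in patients with complete, durable donor chimerism.

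**Conclusion.** The concern holds. The table ends at 20, the CBU cohort goes to 60, and neither addendum adds a count, so the primary safety limit has no count-based decision for up to two thirds of the cohort. At least 25 of those patients were still to be treated at the May 2020 amendment if the cap of 35 was kept. If neither the pause nor the DSMB ends accrual, a cohort that passed 20 finishes above 10% with probability 68% at a true 15% and 91% at a true 20%.

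These figures assume one complication, a constant rate, independent patients and outcomes known at each look. The statement that the rules had not been met by May 2020 is not disputed. This should be fixed; it does not mean that monitoring was absent.

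**What to change.** Extend the section 10.2 table to 60 treated. Read it at the existing five-patient DSMB reports, starting with the next one, using cumulative CBU counts over treated patients (section 10.3 already bases the sample size on treated). Say how patients before and after the May 2020 prophylaxis change are handled. Reconcile sections 8.3, 10 and 10.2 on which of the primary complications trigger the pause.

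The documents do not determine the extension, so the sponsor should choose its strictness and report the operating characteristics. Examples 1 and 2 are illustrations only. Neither is a strict 10% line: they let 8/60 (13%) and 11/60 (18%) continue. Jeffreys cutoffs from 0.802 to 0.856 all reproduce the current columns but extend slightly differently (0.82 gives 4/25 and 7/50).

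The cost in text is up to eight columns and a few sentences. The statistical cost at an acceptable true rate of 10% is:

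| | Example 1 | Example 2 |
|---|---|---|
| Looks 25-60: later stop given pass 20 | 16% | 3% |
| Unconditional addition per complication | 11 points | 2 points |
| Two independent complications, overall stop (now 1 − 0.686² = 53%) | 67% | 56% |
| First new look at 40: later stop given pass 20 | 15% | 1.5% |
| Unconditional addition per complication | 10 points | 1 point |
| Two independent complications, overall stop | 66% | 54% |

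At a true 5%, the addition is at most 1 point per complication. By contrast, a strict line above 10% from 25 onward (3/25, 4/30, 4/35, 5/40, 5/45, 6/50, 6/55, 7/60) would stop 51% of true-10% cohorts that passed 20, or 35 points unconditionally. That is why strictness needs a deliberate choice.

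### The stopping table at 15 and 20 patients triggers only at an observed 20%, so not meeting it does not show that the 10% safety limit in Section 10 was respected

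*Combined protocol and SAP*

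**What the plan says.** Section 10 defines safety, the primary objective, by two complications, each with a 10% ceiling. For grade III-IV GVHD, an incidence above 10% "of this complication in either cohort will be considered unacceptable". For unexplained prolonged myelosuppression, an incidence above 10% "of this complication will also be considered unacceptable".

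The text of Section 10.2 turns this into a rule on observed counts. "If more than one patient out of 10 enrolled patients" in a cohort has either complication, the cohort stops, and the text itself equates that count with more than 10%. It adds an early rule: "if three or more of the first five patients in a particular cohort experiences either of these complications, the cohort will also be stopped".

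A table is then offered as an illustration. Its rows "No with gr III-IV GVHD to trigger stopping rules" and "No with prolonged myelosuppression to trigger stopping rules" both read 2, 2, 3 and 4 at 5, 10, 15 and 20 treated patients. The row for either complication has an entry (3) at 5 patients only. The table ends at 20. No derivation or error rate is given for the counts.

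The addendum of 26 May 2020 closes the section: "To date stopping rules have not been met in the CBU cohort after enrolling more than 30 patients". On the same occasion Section 10.1 raised CBU accrual to 60 treated patients.

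**The concern.** At 10 patients, text and table agree: 2 is the first whole number above 10% of 10. At 15 and 20 patients the table is one event looser than the limit it is said to illustrate. The same data, for example 3 of 20 in the cohort as first sized, are above the ceiling in Section 10 as an observed rate, yet are a continue under Section 10.2. The documents do not say which statement governs.

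What is at stake is how the primary safety result is read. A cohort can finish with an observed rate above 10% and still be described, correctly, as having met no stopping rule. The May 2020 addendum makes a statement of this kind for the CBU cohort at the point where accrual is extended.

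**Working it through.** **Inputs.** Ceiling: above 10% for each complication (Section 10). Triggers: 2/2/3/4 at 5/10/15/20 for each complication (Section 10.2 table). First planned size: about 20 per cohort (Section 10.1).

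**The plan's own figure.** The only derived number in these sections is the interval half-width of 13.1% in Section 10.1: 1.96 × √(0.10 × 0.90 / 20) = 0.1315. It is reproduced, apart from rounding.

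**Table entries as observed rates.**

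| Patients | Trigger | Rate at trigger | First count above 10% | Its rate |
|---|---|---|---|---|
| 5 | 2 | 40% | 1 | 20% |
| 10 | 2 | 20% | 2 | 20% |
| 15 | 3 | 20% | 2 | 13.3% |
| 20 | 4 | 20% | 3 | 15% |

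Two of 15 passes if at most 1 event fell in the first 10 patients. Three of 20 passes if at most 1 fell in the first 10 and at most 2 in the first 15. Both paths are possible.

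**Probability of stopping by patient 20, one complication.** Events are taken as independent between patients with a constant true rate p. Start with 0 events. For each successive block of five patients, add a Binomial(5, p) count to the running total, remove the probability at or above the trigger as stopped, and carry the rest forward. The stopping probability is the sum of what was removed. At p = 10% with the table's triggers, the four looks remove 0.0815 + 0.1824 + 0.0345 + 0.0155 = 0.314. The comparison uses 2/2/2/3, which applies the observed-above-10% rule at 15 and 20.

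| True rate | Table 2/2/3/4 | 2/2/2/3 |
|---|---|---|
| 5% | 9.6% | 18.0% |
| 10% | 31.4% | 48.1% |
| 15% | 55.1% | 72.2% |
| 20% | 74.3% | 87.0% |

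The table therefore fails to stop in 100 − 55.1 = 45% of cohorts at a true 15%, and in 100 − 74.3 = 26% at a true 20%. The chance of ending at exactly 3 of 20 without a stop is 7.7%, 9.8% and 8.3% at true rates of 10%, 15% and 20%.

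**Both complications together.** Either complication can stop the cohort. If the two are independent and each has a true rate of 10%:

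- table: 1 − (1 − 0.314)² = 53%
- 2/2/2/3: 1 − (1 − 0.481)² = 73%

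The entry of 3 for either complication at 5 patients does not change this. Three patients with at least one complication means that one of the two has occurred at least twice, which already triggers its own row.

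**What the observed rates show.** Exact 95% intervals are 1.7% to 40.5% for 2 of 15, and 3.2% to 37.9% for 3 of 20.

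**The case against.** The best defence is that a monitoring boundary need not equal the rate called unacceptable. Setting it higher limits false stops, and the calculation bears this out: the tighter counts would stop 48% of cohorts whose true rate is exactly 10%, against 31% for the table. Section 10 speaks of an incidence, not of every observed proportion, and Section 10.1 frames the cohort as estimation with a confidence interval. Neither 2 of 15 nor 3 of 20 shows a true rate above 10%. All of this stands, and it is why the counts need not change. It does not remove the inconsistency, because the plan gives no such reason and its own text at 10 patients applies the ceiling directly to the observed count.

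Other safeguards exist. Life-threatening, ICU-level or fatal events suspend enrolment (Section 10.2), and the DSMB receives reports after every five patients per arm (Section 13). Such cases would not go unreviewed. But these safeguards do not apply the 10% limit, and enrolment may resume on the investigators' own assessment.

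The looks at 15 and 20 are already past for the CBU cohort, so new table entries could act only on the haplo cohort, which had not accrued by May 2020. This also stands. For CBU, what matters is reporting.

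A reader might go further and infer that the CBU cohort exceeded 10%, or that the addendum sentence is the protocol's only safety information. The documents support neither. The reviewed text gives no CBU counts. Section 5.5, amended on the same date, reports a high incidence of grade 3 and 4 acute GVHD among the minority with complete, durable donor chimerism. Section 2.6 (preliminary results) is not in the reviewed text and may contain the counts.

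**Conclusion.** The concern holds as an inconsistency between the ceiling and the table, and as a limit on what the May 2020 sentence can show. At 15 and 20 patients the table triggers one event above the first count that exceeds 10%. Not triggering is compatible with an observed 13.3% or 15%. For one complication it is also compatible with true rates well above the ceiling: no stop in 45% of cohorts at 15% and in 26% at 20%. The table also ends at 20, while the sentence covers more than 30 patients.

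These figures assume that the table is applied as printed at all four looks, that each complication is counted separately, and that patients are independent with a constant rate. The figures for both complications further assume that the two are independent of each other.

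It would be tempting to conclude that the entries must become 2 of 15 and 3 of 20, or that a fixed verdict such as 7 or more of 60 (11.7%) should be imposed. Neither follows. The first raises stopping at an acceptable true 10% to 48% per complication and about 73% for both. The second would call a true 10% rate unacceptable 39% of the time (binomial, 60 patients). This is a should-fix point: the primary safety criterion needs one consistent reading, but no breach is shown and the study is a pilot without a formal test.

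**What to change.** Reconcile the text and table of Section 10.2 with Section 10. At minimum:

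1. Keep the counts, but label the 15- and 20-patient entries as early-stop triggers at an observed 20% or more.
2. State their operating characteristics: at a true 10%, a 31% chance of stopping per complication and about 53% for both if independent; no stop in 45% at a true 15% and in 26% at a true 20%, per complication.
3. Say that not triggering does not establish that the 10% limit is met.
4. For each cohort and each complication, report the final count, denominator and exact 95% confidence interval against 10%.
5. Accompany the May 2020 sentence with the CBU counts and denominators, unless Section 2.6 already gives them.

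The sponsor may instead tighten the entries to 2 of 15 and 3 of 20, in effect for the haplo cohort only. This is a choice rather than a required correction, given the higher chance of stopping an acceptable cohort.

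The minimum version costs protocol wording, one tabulation of data already held, and a less favourable safety statement.
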